### 3. OBJECTIVES, ESTIMANDS, AND ENDPOINTS

Objectives	Estimands	Endpoints
Primary:	Primary:	Primary:

To characterize the safety profile of tafamidis once daily for the treatment of Chinese ATTR-CM patients in clinical practice.

	

Not applicable.

	

Incidence of treatment-emergent adverse events.

Secondary:		Secondary:

To characterize the descriptive efficacy of tafamidis once daily in Chinese ATTR-CM patients.

To characterize tafamidis PD in Chinese ATTR-CM patients.

To characterize the impact on quality of life of tafamidis once daily for the treatment of Chinese ATTR-CM patients.

To characterize tafamidis PK in Chinese ATTR-CM patients.

	

Not applicable.

	

Assessment of 6-MWT, NT-pro BNP at scheduled visits.

TTR stabilization and TTR concentration at baseline (pre dosing) on Day 1, at Months 1, 6, and 12 (or End of Treatment (EOT)).

Kansas City Cardiomyopathy Questionnaire overall summary scores, EQ-5D-5L index scores and EQ-5D VAS scores, 12-Item Short Form Survey (SF-12) scores, at Day 1, Months 6, 12 (or End of Treatment (EOT)).

PK: plasma concentrations of tafamidis at Months 1, 6, and 12 (or EOT).

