### **7. DISCONTINUATION OF STUDY INTERVENTION AND PARTICIPANT DISCONTINUATION/WITHDRAWAL**

#### **7.1. Discontinuation of Study Intervention**

Participants with one or more of the following criteria in the study duration will discontinue the investigational drug:

Experience adverse events that may be associated with the tolerability of treatment with tafamidis, other safety criteria(eg, AE, PK criteria), disease state criteria (eg, progressive disease), etc. The site has the option to discontinue dosing for this participant and to terminate the participant's study participation.

Note that discontinuation of study intervention does not represent withdrawal from the study unless the patient requests withdrawal from the study. If study intervention is definitively discontinued, the participant will remain in the study to be evaluated for the End of Treatment visit (within 2 weeks after the End of Treatment date). See the [SoA](#) for data to be collected at the time of discontinuation of study intervention and follow-up for any further evaluations that need to be completed. In the event of early Study Intervention Discontinuation, the site staff will follow-up on the participant's vital status at Month 12 from baseline (or at Early Study Discontinuation visit for a participant who withdraws consent for any further contact).

In the event of discontinuation of study intervention, it must be documented on the appropriate CRF/in the medical records whether the participant is discontinuing further receipt of study intervention or also from study procedures, posttreatment study follow-up, and/or future collection of additional information.

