#### **9.2. Sample Size Determination**

In order to attain an 80% probability of observing at least 1 participant having an event for TEAEs with incidence rate of 3%, at least 53 participants need to be treated.

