### **3.2.4. Quality of Life Endpoints**

All quality of life endpoints will be assessed at baseline, Month 6 and 12 (or EOT)

- Change from baseline in the Kansas City Cardiomyopathy Questionnaire Overall Summary scores (KCCQ-OS)

Changes from baseline in the KCCQ domain scores (Physical Limitation, Symptom Stability, Symptom Frequency, Symptom Burden, Total Symptom, Self-efficacy, Social Limitation, and Quality of Life) and Clinical Summary Score are also included as endpoints.

Total Symptom Score is calculated as the mean of Symptom Frequency and Symptom Burden Scores. Clinical Summary Score is calculated as the mean of Physical Limitation Symptom Frequency and Symptom Burden Scores. Overall Summary Score is calculated as the mean of Physical Limitation, Symptom Frequency, Symptom Burden, Quality of Life, and Social Limitation Scores.

- Change from baseline in Short-Form Survey 12 (SF-12, version 2, Acute) score

The 12-item Short Form Scale scores are summed into 2 scales: physical component summary score (PCS) and mental component summary score (MCS). In addition, 8 sub-scale scores are also included as endpoints: physical function (PF), role physical (RP), role emotional (RE), mental health (MH), bodily pain (BP), general health (GH), vitality (VT), and social function (SF). Higher scores indicate better quality of life.

- Change from baseline in EuroQol 5 Dimensions 5 Levels (EQ-5D-5L) index score and visual analog scale (VAS) scores

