## 5. GENERAL METHODOLOGY AND CONVENTIONS

### 5.1. Hypotheses and Decision Rules

This is an estimation study with no statistical hypothesis nor decision rules.

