#### **6.6.2. Study Conduct and Participant Disposition**

The end of treatment subject disposition will be shown. Frequency/counts will be provided for subject discontinuation(s) and completion.

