### Appendix 1. Data Derivation Details

#### Appendix 1.1. Definition and Use of Visit Windows in Reporting

To maximize the use of all available data, the analysis visit windows are expanded. For endpoints with post-baseline assessments at Month 1, 6 and 12 (except PK endpoints), the analysis windows are defined in below table. The study day will be calculated as: date of assessment/collection – date of the first dose + 1. If two or more visits/observations fall into the same window, the visit / observation closest to the target day should be used in the analyses. If there is a tie, the later visit should be used. Note: for ECG and Echocardiogram, the central laboratory reading data takes priority. For NT-proBNP, TNI and RBP, only the central laboratory reading data are included in analysis.

Visit Label	Target Day	Definition [Day Window] - Lower	Definition [Day Window] - Upper
-------------	------------	---------------------------------	---------------------------------

Baseline	1	Day 1 = date of first dose of study treatment taken in the study  Prior to first dose of study treatment taken in the study	
Month 1	31	16	105
Month 6	181	106	270
Month 12	361	$\geq 271$ (Note: Set upper at Day 375 for PD endpoints)	

For endpoints with post-baseline assessments only at Month 6 and 12, the analysis visit windows are defined as below.

Visit Label	Target Day	Definition [Day Window] - Lower	Definition [Day Window] - Upper
Baseline	1	Day 1 = date of first dose of study treatment taken in the study  Prior to first dose of study treatment taken in the study	
Month 6	181	91	270
Month 12	361	$\geq 271$	

For PK, tafamidis concentrations will be measured at Month 1 pre-dose and 3 hours ( $\pm 1.5$  hours) post-dose; Month 6, 7 hours ( $\pm 2.5$  hours) post-dose; Month 12, 1 hour ( $\pm 30$  minutes) post-dose. The PK sampling windows are defined in below table. The sampling time window will be calculated as: time of sample collection – time of dosing of most recent study treatment.

Visit Label	Planned Time Post Dose (hours)	Definition [Time Window] – Lower (hours)	Definition [Time Window] – Upper (hours)
Month 1	0 (Pre-dose)	Prior to dosing of study treatment on the sample collection day	
Month 1	3	1.5	4.5
Month 6	7	4.5	9.5
Month 12	1	0.5	1.5

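### SAP Appendix 1.1 has no End-of-Treatment rule, so some EOT values enter no by-visit summary and the quality-of-life time point Month 12 (or EOT) is only partly produced

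*SAP*

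**What the plan says.** **Endpoint definitions.** For quality of life, Protocol section 3 specifies "12-Item Short Form Survey (SF-12) scores, at Day 1, Months 6, 12 (or End of Treatment (EOT", and SAP 3.2.4 agrees: "All quality of life endpoints will be assessed at baseline, Month 6 and 12 (or EOT". For 6-MWT and NT-proBNP, Protocol section 3 refers only to scheduled visits, and SAP 3.2.1 names baseline, Month 6 and Month 12. SAP 3.4 names the same post-baseline visits for troponin I and NYHA.

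**Collection.** Protocol 4.1 counts Month 12 or End of Treatment as one scheduled visit. The Schedule of Activities puts all of these assessments in a single column, headed Month 12 or within 2 weeks after End of Treatment. Under Protocol 7.1, when drug is definitively stopped, "the participant will remain in the study to be evaluated for the End of Treatment visit". After that, section 7.1 provides for vital status at Month 12.

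**Analysis.** SAP 6.2 and 6.4 summarize by analysis visit or time point. SAP 5.3 imputes no missing values for these summaries. Appendix 1.1 assigns values by study day. It states: "For endpoints with post-baseline assessments only at Month 6 and 12, the analysis visit windows are defined as below". The table below that sentence gives Month 6 (target Day 181, Days 91-270) and Month 12 (target Day 361, Day 271 onward). When two observations share a window, "the visit / observation closest to the target day should be used in the analyses", and a tie goes to the later one. The appendix states that the windows were widened to make the most of the available data.

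**The concern.** The EOT visit is normally the last occasion on which an early stopper has a 6-MWT, cardiac biomarkers or questionnaires. If the windows pass over that value, no later one replaces it. Applied exactly as written, the SAP cannot fully deliver the quality-of-life time point that both documents define, and it leaves measured data out of the summaries despite the appendix's stated aim.

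The omission may not be random. Protocol 7.1 gives adverse events and progressive disease among its examples of reasons to stop drug. The study tests no hypothesis (SAP 5.1: "This is an estimation study with no statistical hypothesis nor decision rules"), so these descriptive tables are the efficacy and quality-of-life result. No longitudinal model is planned that would use the omitted values.

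**Working it through.** **The plan's own figures.** Protocol 9.2 asks for an 80% chance of seeing at least one event with 3% incidence. 1 - 0.97^53 = 0.801 and 1 - 0.97^52 = 0.795, so N = 53 is reproduced. The window limits are the midpoints between target days: (1 + 181)/2 = 91 and (181 + 361)/2 = 271, which match the table. Neither figure is in question.

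**Inputs.** Windows, target days and the tie rule come from SAP Appendix 1.1. The EOT visit within 2 weeks of stopping comes from Protocol 7.1. The dropout rate and timing are not given; SAP 6.6.2 says only "Frequency/counts will be provided for subject discontinuation(s) and completion". Stop timing is therefore an assumption throughout, and no further on-study assessment is assumed after EOT.

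**Step 1: where an EOT value goes.** Take the Month 6 visit as held on Day 181 if the participant is still on drug, and EOT on any of Days 2-360 (359 days).

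| EOT day | Days | Treatment under Appendix 1.1 |
|---|---|---|
| 2-90 | 89 | No window, not summarized |
| 91-181 | 91 | No earlier Month 6 visit, summarized as Month 6 |
| 182-270 | 89 | In the Month 6 window but farther from Day 181 than the held visit, not summarized |
| 271-360 | 90 | Summarized as Month 12 |

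Unused: (89 + 89)/359 = 178/359 = 49.6%. Summarized as Month 6: 91/359 = 25.3%. Summarized as Month 12: 90/359 = 25.1%.

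**Step 2: alternative day count.** Count only Days 1-346, before the Month 12 visit window opens. The four cells become 90, 91, 89 and 76 days, so (90 + 89)/346 = 179/346 = 51.7% is unused.

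**Step 3: a Month 6 visit off target.** If it is held on Day 167, an EOT value up to Day 195 is nearer or tied and displaces the Month 6 value. EOT values on Days 196-270 (75 days) are still lost. Unused: (89 + 75)/359 = 164/359 = 45.7%.

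**Step 4: other stop patterns.** Stop times were simulated with an EOT lag of 0 or 0-14 days and the Month 6 visit on Day 181 or within 14 days of it. Ranges are over those settings.

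| Assumed stop pattern | EOT values unused | EOT values reaching Month 12 |
|---|---|---|
| Uniform | 45-52% | 22-27% |
| More late stops | 35-40% | 39-42% |
| Exponential, half-time 180 days | 55-59% | 12-14% |
| Exponential, half-time 90 days | 62-67% | 6-7% |

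**Step 5: illustration of scale.** If 10-20% of 53 participants stopped early, 5-11 would have EOT visits, and about half (3-5) would enter no summary. The shift in a mean is the omitted fraction times the gap in change. With an assumed 70 m gap in 6-MWT, that is 3/53 x 70 = 4.0 m to 5/53 x 70 = 6.6 m. Neither the dropout rate nor the gap comes from the documents.

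**The case against.** Several points on the other side stand.

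- **Not mostly dropped.** A reader might infer that most EOT values are lost. Under uniform stopping it is about half, and a clear majority only if stops cluster early. The documents do not say when stops will occur.
- **Not absent altogether.** A reader might infer that Month 12 (or EOT) is never produced. EOT values from Day 271 do enter the Month 12 row, and EOT values on Days 91-270 with no Month 6 visit enter the Month 6 row.
- **Not erased.** SAP 6.2 lists individual values for 6-MWT, NT-proBNP and quality of life, and a handful of cases among about 53 can be read there. SAP 6.4 makes no such statement for troponin I and NYHA.
- **The EOT wording is specific to quality of life.** For the other endpoints the schedule governs collection, and no protocol text tells the analyst to pool an early EOT value with Month 12. SAP 2.1 is silent on EOT, but this is better described as incomplete implementation than as an undeclared change.
- **Bias towards stability is not shown.** Progressive disease is only one example in section 7.1. Participants who die, are lost or refuse follow-up may supply no EOT value at all. A value from about Day 40 has had little time to decline, so calling it Month 12 acts like carrying the last value forward and can itself flatter the result. Keeping it out of the Month 12 row is a defensible observed-case choice.

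The last point limits the form of the remedy. None of them explains why a defined quality-of-life time point has no complete derivation rule.

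**Conclusion.** The concern holds in limited form. Appendix 1.1 has no EOT row or rule. EOT values before Day 91, or after a held Month 6 visit and up to Day 270, are generally left out of every by-visit summary. This is an inconsistency with the stated definition for quality of life. For 6-MWT, NT-proBNP, troponin I and NYHA it is a loss of scheduled, measured data rather than a breach of the endpoint wording.

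The share unused is about half if stops are uniform and 35-67% across the patterns tried. How many participants this means, and whether the summaries lean towards stability or decline, cannot be settled from the documents. The affected endpoints are secondary or other efficacy endpoints and are descriptive. The incidence of treatment-emergent adverse events and the sample size do not depend on these windows. The SAP should be clarified, because the gap is real and cheap to close.

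**What to change.** In SAP Appendix 1.1 and 6.2 (with 6.4 for troponin I and NYHA), keep the Month 6 and Month 12 rows exactly as they are and add one separately labelled supplementary row:

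- **KCCQ, EQ-5D-5L and SF-12:** a *Month 12 or EOT* row that uses the Month 12 assessment if there is one and otherwise the EOT assessment, whatever its study day.
- **6-MWT, NT-proBNP, troponin I and NYHA:** an *EOT/last on-study value* row, or the same *Month 12 or EOT* row.

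For each, report the number of participants contributing an EOT value and the study days of those values. Footnote that an EOT value may also appear in the Month 6 or Month 12 row.

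The cost is SAP wording and one extra row per table (an extra panel for the NYHA shift table), with no new data. The downside is that the row mixes follow-up times, and very early EOT values can understate decline. It should therefore supplement the Month 12 row and not replace it.

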## Appendix 2. List of Abbreviations

Abbreviation	Term
6-MWT	6-minutes walk test
AE	Adverse event
ATTR-CM	Transthyretin amyloid cardiomyopathy
ATTR-PN	Transthyretin Amyloid Polyneuropathy
BMI	Body Mass Index
BP	Body pain
CI	Confidence interval
cTNT	Cardiac troponin T
cTNI	Cardiac troponin I
CV	Coefficient of variation
E/A	Ratio of peak velocity blood flow from gravity in early diastole (the E wave) to peak velocity flow in late diastole caused by atrial contraction (the A wave).

---

Abbreviation	Term
ECG	Electrocardiogram
EOT	End of Treatment
EQ-5D VAS	EuroQoL 5 Dimensions visual analogue scale
EQ-5D-5L	EuroQoL 5 Dimensions 5 Levels
FOI	Fraction of initial tetramer concentration
KCCQ	Kansas City Cardiomyopathy Questionnaire
mBMI	Modified Body Mass Index
MCS	Mental component summary score
MH	Mental health
NT-proBNP	N Terminal prohormone B type Natriuretic Peptide
NYHA	New Year Heart Association
PCS	Physical component summary
PD	Pharmacodynamics(s)
PK	Pharmacokinetic(s)
PR	PR interval
QD	Once daily
QRS	QRS complex
QT	QT interval
QTc	Corrected QT
QTcF	Corrected QT (Fridericia method)
RE	Role emotional
RP	Role physical
SAE	Serious adverse event
SAP	Statistical analysis plan
SF	Social function
SF-12	12-short item survey form
TEAE	Treatment-emergent adverse events
TnI	Troponin I
TTR	Transthyretin
